7.3.2 Primary Safety Criterion

The primary safety criterion is diagnosis of SCC (defined as invasive SCC, i.e. excluding SCC in situ) in the treatment field across the 3-year trial period. Invasive SCC is diagnosed by biopsy.

The CCTP states: “*The 3-year cumulative incidence will be calculated for each treatment group using methods of survival analysis for estimation of cumulative incidence in the presence of censored time-to-event data. Annual incidence rates will also be presented for each group. The cumulative incidence rates will be presented for the event of SCC as primary endpoint and for SCC and other neoplasia as secondary. No formal statistical test comparing the two arms will be performed. For descriptive purposes, as an additional analysis, the difference in cumulative incidence rates between the two arms will be estimated and presented together with its 95% confidence interval.*”

The time to first SCC in months will be calculated as days divided by the average number of days in a month:

$$(\text{Date of biopsy} - \text{date of first exposure to trial medication})/30.4375$$

The cumulative incidence rate with 95% confidence intervals (CIs) will be estimated for each treatment group using SAS *PROC LIFETEST* where the *STRATA* statement will include the randomisation stratification factors *country, anatomical location, and history of SCC*, and with the option *GROUP=treatment*. The incidence rates will be presented using the option *TIMELIST=12 24 36* for 1, 2 and 3 years, respectively. Cumulative incidence will be presented by 1 minus the survival curves estimated using the Kaplan-Meier method. Moreover, numbers at risk and censoring information will be presented by treatment group.

The analysis will be presented for the safety analysis set. In addition, the analysis will be presented for the PP analysis set using PP censoring as described in section 7.3.1. Please see the analysis set definition document for details.

The additional analysis of difference in the 3-year cumulative incidence rates will be calculated as the difference between the Kaplan-Meier estimates of each treatment group and will be presented with 95% CI. The difference is assumed to be approximately normally distributed, and as the treatment groups are assumed to be independent and identically distributed, the 95% CI will be calculated as $\pm 1.96 \times \sqrt{(SE_{Ing}^2 + SE_{Imi}^2)}$ where SE_{Ing} and

Trial ID: LP0041-63	Date: 28-AUG-2019	Version: Final 1.0 Page 11 of 32
---------------------	--------------------------	-------------------------------------

SE_{imi} are the standard errors (SEs) of the Kaplan-Meier estimates in the ingenol mebutate and imiquimod groups, respectively.

Suspicion of SCC or other neoplasia (Yes/No) will be summarised by visit. The results of biopsies will be summarised by visit and by country.

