**Number of subjects entered:**

A total of 480 subjects will be enrolled in the trial and randomised in a 1:1 ratio to the two treatment groups. With 240 patients in each treatment group an adequate precision of the 3-year incidence rate can be obtained. Assuming a 3-year rate of 1.0%, the upper 95% confidence limit will on average be 2.26%, and assuming a 2.5% rate, the upper 95% confidence limit will on average be 4.48%,

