### 3.1.2 Follow-up Period

Visit Number	11	12	13	14	15	16
Week/Month (window)	Week 20 (±14 days)	Month 12 (±14 days)	Month 18 (±28 days)	Month 24 (±28 days)	Month 30 (±28 days)	Month 36 (±28 days)
Concomitant medications, treatments, procedures	X	X	X	X	X	X
Field assessment for SCC, BCC or neoplasia	X	X	X	X	X	X
Adverse events	X	X	X	X	X	X
AK count	X	X	X	X	X	X
Brief physical exam 		X	X	X	X	X

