#### Visit 16 (Month 36 ± 28 days)

Visit 16 will include:

- Clinical assessment of neoplasia in the selected treatment area (biopsy if there is suspicion of SCC, BCC or other neoplasia)
- Dermatologic examination of selected treatment area including AK count
- Reporting of (S)AEs (see [Table 3](#))
- Reporting of concomitant medication, treatments and procedures
- Abbreviated physical examination

[figure not shown]

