### **10.9.1 Primary Response Criterion**

Diagnosis of SCC (defined as invasive SCC i.e. excludes SCC in situ) in the treatment field across the 3-year trial period

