7.3.1 Censoring

Since the primary and secondary safety criteria are time-to-event analyses, a censoring scheme will be defined. This is not detailed in the CCTP.

Subjects from the safety analysis set will be included in the time-to-event analyses, as described in [Table 1](#):

Table 1: Censoring

Event	Date	Outcome
SCC	Date of biopsy	Event
Missing result from a biopsy	Date of biopsy	Censored
Trial completion without SCC	Date of last visit with assessment and no SCC	Censored
Trial discontinuation	Date of last visit with assessment and no SCC	Censored
Death from any cause	Date of death	Censored

SCC: Squamous cell carcinoma

In addition, a PP censoring will be defined, which is censoring at the time when a subject is excluded from the PP analysis set, as described in [Table 2](#):

Table 2: PP censoring

Event	Date	Outcome
Exclusion from PP analysis set with no documented SCC	Date of last visit with assessment before exclusion with no SCC	Censored

PP: Per protocol, SCC: Squamous cell carcinoma

Details on censored subjects are given by subject ID in the analysis set definition document.

Trial ID: LP0041-63	Date: 28-AUG-2019	Version: Final 1.0 Page 10 of 32
---------------------	--------------------------	-------------------------------------

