7.3.3 Secondary Safety Criterion

The secondary safety criterion is diagnosis of SCC and other neoplasia in the treatment field over a 3-year period and will be analysed like the primary safety endpoint.

SCC and other neoplasia are diagnosed by biopsy and include the following diagnoses

- Invasive SCC
- Basal Cell Carcinoma (BCC)
- In Situ BCC/Bowen
- Other neoplasia

The diagnoses “Actinic Keratosis” and “No malignant findings” are not neoplasia events.

The analysis will be presented for the safety analysis set. In addition, the analysis will be presented for the PP analysis set using PP censoring. Please see the analysis set definition document for details.

The CCTP states

“A landmark analysis, conditional on patients’ responses at Week 20, will additionally be performed in order to exclude SCC and other neoplasia reported within the first 20 weeks which are not assumed to be associated with the study treatment. Patients who experience a neoplasia before the 20-week landmark time point are excluded from the time-to-event analysis, which is otherwise conducted as above.”

Diagnosis of SCC and other neoplasia in the treatment field from Week 20 onward will be analysed as described above.

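### The 3-year SCC incidence is read at day 1095.75 on actual dates, so an SCC found at a valid Month 36 visit is dropped or over-weighted depending on the appointment day

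*SAP*

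**What the plan says.** The primary endpoint (Protocol 10.9.1) is invasive SCC "in the treatment field across the 3-year trial period". SAP 7.3.2 defines the time scale: "The time to first SCC in months will be calculated as days divided by the average number of days in a month", where days run from first exposure to the biopsy and the divisor is 30.4375. It then states: "The incidence rates will be presented using the option *TIMELIST=12 24 36* for 1, 2 and 3 years, respectively". The arm difference is taken from the same 36-month Kaplan-Meier values.

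In SAP 7.3.1, Table 1, a subject who completes without SCC is censored at "Date of last visit with assessment and no SCC", which is the actual date of the final visit. Protocol 10.1.3 lists that visit as "Visit 16 (Month 36 ± 28 days"), with a neoplasia assessment and a biopsy on suspicion. The schedule in Protocol 3.1.2 gives the same window.

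Neither document assigns the Month 36 visit a nominal time or gives a rule for an SCC found in the window after the reading point. SAP 7.5.3 allows no imputation beyond the censoring rules. The Analysis Set Definition Document was not available; the SAP cites it for analysis sets and censored subjects, not for visit timing.

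Shell 5 prints the crude SCC count and the cumulative incidence together without a reading time. Its title runs to the end of the trial, while Appendix I lists the same tables as running to Month 36. Shells 6 and 9 do state Month 36.

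**The concern.** About half of the valid eight-week window lies after the reading point. A subject who attends on schedule and has a biopsy-confirmed SCC can be a primary event in the counts and listings yet contribute zero to the primary estimate. A similar subject seen a day earlier contributes more than one subject's share, because completers seen earlier in the window have already left the risk set.

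At 12 and 24 months this does little harm: follow-up continues, and a late event appears at the next reading. At 36 months there is no next reading, so the loss is permanent. With so few SCCs expected, appointment dates can visibly move the headline figure and the arm difference.

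**Working it through.** **The plan's precision figures.** Inputs from Protocol 10.3: 240 per arm, true 3-year rates 1.0% and 2.5%. The formula p + 1.96·√(p(1−p)/240) gives:
- p = 0.010: 1.0% + 1.26% = 2.26%
- p = 0.025: 2.5% + 1.98% = 4.48%

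Both match the Protocol. The formula treats all 240 as fully observed, so each SCC weighs 1/240 = 0.417 points. Expected SCCs per arm are 240 × 0.010 = 2.4 and 240 × 0.025 = 6.

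**The cut.** 36 × 30.4375 = 1095.75 days. The window is 1095.75 ± 28 = 1067.75 to 1123.75. Day 1095 is 35.975 months and counts; day 1096 is 36.008 months and does not. On the planned calendar (Protocol 10.2), every subject's three years include 29 February 2016, so the exact third anniversary is day 1096 and misses the reading.

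**Weight of one SCC.** Take 240 completers with Month 36 visits spread evenly over the window. The SCC adds to the 36-month estimate:

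| Day of SCC | At risk | Added (points) |
|---|---|---|
| 1068 | 240 | 0.417 |
| 1082 | 182 | 0.549 |
| 1090 | 148 | 0.676 |
| 1095 | 127 | 0.787 |
| 1096 or later | – | 0 |

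On day 1095 that is 0.787/0.417 = 1.9 times nominal. Under other visit patterns the day-1095 weight is 240/194 = 1.2 (late), 240/137 = 1.8 (clustered on target) or 240/59 = 4.1 (early). None of these is a bound.

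**Average effect.** If F is the share of Month 36 visits on or before day 1095, the mean weight of a Month 36 SCC is −ln(1−F): 0.29 at F = 25%, 0.69 at 50%, 1.39 at 75%. About one sixth of SCCs surface at that visit, so F = 50% implies a shift of about (0.69 − 1)/6 = −5%, close to the simulated −6%.

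**Simulation.** Assumptions: 240 per arm, constant hazard, detection at scheduled visits, whole-day dates, and no dropout unless stated; 4,000 arms per scenario. The documents do not report how visits fell, so the visit patterns are assumed. The late and early patterns average 9 days after and before target. Entries are for true rates 1.0% / 2.5%; the shift is relative to the timing proposed below, on the same data.

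| Scenario | Arm loses ≥1 SCC | Mean shift | RMSE, actual dates (points) | RMSE, proposed (points) |
|---|---|---|---|---|
| Uniform | 20% / 42% | −6% / −6% | 0.64 / 1.01 | 0.64 / 1.00 |
| Clustered | 19% / 41% | −6% / −6% | 0.64 / 0.99 | 0.64 / 1.00 |
| Late | 26% / 56% | −12% / −13% | 0.62 / 0.99 | 0.64 / 1.00 |
| Early | 10% / 22% | +7% / +7% | 0.78 / 1.19 | 0.65 / 1.01 |
| Uniform, 15% dropout | 17% / 37% | −6% / −6% | – | – |
| Uniform, half of SCCs found between visits | 11% / 25% | −3% / −3% | – | – |

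With uniform visits the shift is about −0.06 / −0.15 points, against planned half-widths of 1.26 / 1.98. The arm difference moves by at least 0.35 points in 30% / 50% of trials (19% / 37% if half of SCCs are found between visits), with no built-in direction. An arm with at least one SCC shows 0.0% at 36 months in 2.1% / 0.2% of arms. With visits about 15 days late or early, the mean estimate is 0.84% or 1.24% for a true 1.0%, and 2.12% or 3.02% for a true 2.5%.

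**The case against.** Reading an actual-date Kaplan-Meier curve at 36 months is a literal implementation of a 3-year cumulative incidence. A biopsy at 36.5 months is, by its date, after three years, and the documents do not say that the trial period extends to the end of the final visit window. The average bias is small, and RMSE is essentially unchanged or slightly better under the SAP's method unless visits run early. No formal test or decision threshold depends on the result; in simulation, whether the interval for the difference excludes zero changes in only about 1% to 4% of trials. A late SCC remains visible in the counts of Shells 5 and 8, the person-year rate of Shell 7, the biopsy summaries by visit and Listing 7-7. The SAP is dated August 2019 for an open-label trial planned to finish in Q2 2018, so replacing the main analysis carries its own risk. Re-timing Visits 12 and 14 also goes further than the 36-month problem requires.

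Much of this stands. It limits the size of the harm and argues for reporting both analyses. It does not remove the problem: showing a case in another table does not put it into the primary estimate, and a protocol-compliant final assessment is most naturally part of the 3-year period. Re-timing Visit 16 alone gives the same 36-month result; including Visits 12 and 14 only aligns the annual readings.

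**Conclusion.** The concern holds. The rule follows directly from the SAP text, and nothing in either document corrects it. A confirmed SCC at a valid Month 36 visit can weigh nothing or nearly twice its share (uniform visits), according to the appointment day. The harm is arbitrary weighting of very few events and a modest bias, not a large loss of accuracy. The mechanism needs no assumption. The size rests on assumed visit timing, constant hazard, the share of SCCs found between visits, and dropout. This should be fixed because the affected figures are the trial's primary result and the correction is cheap.

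**What to change.** In the main time-to-event analyses of the primary and secondary safety criteria:
- Place events and censoring arising from in-window Visits 12, 14 and 16, identified by CRF visit number, at exactly 12, 24 and 36 months. Every SCC up to and including the in-window Month 36 assessment, and any biopsy arising from it, then counts at 36 with everyone assessed at that visit still at risk.
- Leave all other dates as they are: other visits, unscheduled biopsies, deaths and early-termination assessments. The one exception is an unscheduled biopsy after day 1095.75 but within the Month 36 window, which counts at 36.
- State in advance the rule for a Visit 16 outside the window (default: actual date), and which time variable the person-years in Shells 6 and 7 use.
- Decide the Week 20 exclusion ("Patients who experience a neoplasia before the 20-week landmark time point are excluded from the time-to-event analysis") on the actual biopsy date. No date before Visit 12 changes, so an early Visit 11 biopsy (days 126 to 139) cannot cross day 140.
- Keep the planned actual-date Kaplan-Meier as a sensitivity analysis.
- Make the Shell 5 title agree with Appendix I and state the reading time in its cumulative incidence row.

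Reading at the end of the window instead is not a remedy, because the risk set empties there. With uniform visits the mean estimate is then 1.7% to 1.9% for a true 1.0%, and 4.3% to 4.8% for a true 2.5%.

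The cost is SAP wording, one derived time variable and one extra sensitivity table per endpoint. Within-window timing at three visits is lost in the main analysis.

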## 8.1 ACTINIC KERATOSIS

Actinic keratosis is a common skin condition visible as thickened, cornified, scaly lesions and characterised histologically by atypical epithelial proliferation (24). Actinic keratoses usually develop on areas that are frequently exposed to the sun (e.g., face, ears, scalp, neck, forearms, and back of the hands). Patients with AK often express embarrassment, worry, and irritation related to the change in appearance of their skin and unsightly nature of the lesions (25, 26). In addition to the emotional strain, AK lesions can be painful and easily traumatised causing bleeding (26, 27, 28, 29).

In population studies performed in the EU and US, reported prevalence rates for AK have been approximately 11-25% of the population, while estimates are higher in Australian studies (up to 60%) (24). Patients with AK tend to have Fitzpatrick type I or II skin (fair skin) which burns with sun exposure and does not tan (28).

In the context of AK, the skin of patients with AKs shows field cancerisation, characterised by the epithelial surface of the photodamaged area being susceptible to the development of additional AKs or a malignancy. This is evidenced by the presence of multiple subclinical and clinically visible AK lesions as well as multifocal preneoplastic changes with genetic mutations (30). There is also increasing evidence that AK represents SCC in situ in its earliest stages (15, 24, 31). Histological evidence shows that contiguous AK is present in 97% of SCC lesions on sun-damaged skin (15). Actinic keratosis is linked epidemiologically to development of SCC (1), and both conditions share specific gene expression (2). If left untreated, AK may regress, or alternatively, may progress to SCC, with significant morbidity and possible lethal outcome (15).

Predicting which AKs may progress to SCC is not possible, nor is the conversion rate for an AK to SCC clear: the transformation rate from an AK lesion to SCC within one year has been reported to be <1:1000 (32). Further mathematical modelling of these data has predicted that for an individual with an average of 7.7 AKs, the probability of at least one transforming within a 10-year period is approximately 10% (33).

Diagnosis of AKs is based upon the clinical presentation (23). When there is doubt as to the clinical differentiation between AKs and SCCs, histological confirmation may be necessary (23).

---

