Further, in the long-term follow up programme, a total of 198 patients who had demonstrated complete clearance of AK lesions (following treatment with ingenol mebutate gel (184 patients) or vehicle (14 patients)) at Day 57 were followed for possible lesion recurrence and also for safety within the selected treatment area: no SCCs were reported for any of the patients in the 12-month period. This trial seeks to further examine the incidence of SCC for up to 3 years after treatment, within a controlled trial environment rather than as a post-marketing surveillance exercise relying on capture of spontaneous reports.

The trial is a phase 4 post-approval commitment to the European Medicines Agency (EMA).

Please see the Summary of Product Characteristics (SmPC) for ingenol mebutate for further non-clinical and clinical information (21).

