### 8.2.2 Imiquimod

Imiquimod is a topical immune response modifier and a 5% formulation has been approved for the treatment of AKs in the US and Europe (Aldara® cream) with a different dosage regimen. The dose regimen in Europe is one application 3 days per week for 4 weeks, with a 4-week treatment pause followed, if necessary, by another 4-week treatment period. The dose regimen in the US is two applications per week for 16 weeks. In this trial, subjects in the imiquimod group will be treated according to the EU dosage regimen.

Imiquimod is an immune response modifier. In animal models imiquimod has been shown to stimulate the immune system by activating antigen-presenting cells such as monocytes/

---

macrophages and dendritic cells to produce interferon and other cytokines and chemokines, which leads to the stimulation of the adaptive immune response.

The safety and efficacy of imiquimod applied 3 times per week for one or two courses of 4 weeks, separated by a 4-week treatment-free period has been demonstrated in two double-blind vehicle controlled clinical trials , (see more information in the SmPC of Aldara®, [Appendix V](#)).

The rate of progression to SCC was reported to be 1.6% (2/128 patients) within one year. There are no data on recurrence and progression rates beyond 1 year ([Appendix V](#)).

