7.5.3 Handling of Drop-outs and Missing Values

Drop-outs will be handled as described in section 7.3.1 for the primary and secondary safety criteria using censoring in time-to-event analyses.

Missing results from biopsies will be handled using censoring as described in section 7.3.1.

Besides this, no imputation will be implemented.

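### The interval for the between-arm 3-year SCC difference has no rule for an arm without events: that arm is treated as known exactly and the printed interval is too narrow (low severity)

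*SAP*

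**What the plan says.** SAP 7.3.2 states that the 3-year difference "will be calculated as the difference between the Kaplan-Meier estimates of each treatment group and will be presented with 95% CI". It then says "The difference is assumed to be approximately normally distributed" and gives the half-width as 1.96×√(SE_Ing² + SE_Imi²), where the two terms "are the standard errors (SEs) of the Kaplan-Meier estimates in the ingenol mebutate and imiquimod groups, respectively". SAP 7.3.3 has the secondary endpoint (SCC and other neoplasia) analysed in the same way, and Tables 2-19 to 2-22 report the differences in the Shell 9 layout.

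Nothing says what to do when an arm has no event. SAP 7.5.3 covers drop-outs and missing biopsies by censoring and ends "Besides this, no imputation will be implemented". SAP 7.5.1, SAP 7.5.6, Shell 9 and Protocol 10.10.6.1 are silent on it.

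Protocol 10.10.6.1 calls the difference an additional, descriptive analysis without a formal test. Protocol 9.1 nevertheless words the primary objective as a comparison of the two cumulative incidences.

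**The concern.** With no event the Kaplan-Meier curve stays at 1 and its standard error is 0. That arm then adds nothing to the width of the interval, as if at most 240 people had fixed its risk at exactly zero. If neither arm has an event, the interval is the single point 0.

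The case is realistic. Protocol 8.2.1 reports on 198 cleared patients, 184 of them treated with ingenol mebutate: "no SCCs were reported for any of the patients in the 12-month period". The planned method would give those 184 a standard error of 0, whereas the Wilson upper limit for 0/184 is 2.05%. That cohort covers cleared patients over 12 months, so it shows that zero counts occur and does not estimate the 3-year rate here.

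The difference is the only planned between-arm estimate for SCC. A descriptive analysis relies on its interval to convey uncertainty. Without a rule, the analyst must either print the degenerate interval or choose a method after seeing the counts.

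**Working it through.** **Inputs.** 240 per arm and 3-year planning rates of 1.0% and 2.5% (Protocol 10.3); interval formula from SAP 7.3.2. The documents give no drop-out rate, so the main figures assume complete follow-up.

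**The plan's own figure.** p + 1.96×√(p(1−p)/240) gives 1.0% + 1.96×0.642% = 2.26% and 2.5% + 1.96×1.008% = 4.48%. Both match Protocol 10.3.

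**Chance of an arm without events.** For one arm it is (1−p)^240: 0.99^240 = 8.96% and 0.975^240 = 0.23%. For at least one arm, a + b − ab:
- 1.0% in both: 2×8.96% − 0.80% = 17.1% (no events in either arm: 0.8%)
- 2.5% vs 1.0%: 0.23% + 8.96% − 0.02% = 9.2%
- 2.5% in both: 0.5%

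If an assumed 10% to 20% of each arm contributed nothing (216 to 192 left), the first figure would rise to 21.5% to 26.9% and the last to 0.8% to 1.5%.

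**Limits at given counts.** Without censoring the Kaplan-Meier SE is √(F(1−F)/n). The comparator is Newcombe's interval. Each arm's Wilson limits l and u are (F + z²/2n ± z√(F(1−F)/n + z²/4n²)) / (1 + z²/n) with z = 1.96. The lower limit for the difference is d − √((F₁−l₁)² + (u₂−F₂)²) and the upper limit is d + √((u₁−F₁)² + (F₂−l₂)²).

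Worked case, 4 vs 0:
- F₁ = 4/240 = 1.667% and SE = 0.826%. The planned interval is 1.667 ± 1.96×0.826 = 0.05 to 3.29, which excludes 0.
- The Wilson limits are 0.65 to 4.21 for 4/240 and 0 to 1.58 for 0/240. The Newcombe lower limit is 1.667 − √(1.017² + 1.575²) = −0.21 and the upper limit is 4.21, so this interval includes 0.

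| Events | Planned (points) | Newcombe (points) |
|---|---|---|
| 0 vs 0 | 0 to 0 | −1.58 to 1.58 |
| 1 vs 0 | −0.40 to 1.23 | −1.20 to 2.32 |
| 2 vs 0 | −0.32 to 1.98 | −0.85 to 2.99 |
| 3 vs 0 | −0.16 to 2.66 | −0.53 to 3.61 |
| 4 vs 0 | 0.05 to 3.29 | −0.21 to 4.21 |
| 5 vs 0 | 0.28 to 3.89 | 0.11 to 4.78 |

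**Coverage.** All pairs of binomial counts were enumerated exactly. The fallback is the planned formula, replaced by Newcombe only when an arm has no event. The lower limit is that for the arm with events minus the arm without.

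| True rates | Overall: planned / fallback | In zero-event samples: planned / fallback | Lower limit misses there: planned / fallback |
|---|---|---|---|
| 1.0%, 1.0% | 95.5% / 97.8% | 76.9% / 90.1% | 23.1% / 9.9% |
| 2.5%, 1.0% | 94.2% / 94.4% | 88.2% / 89.8% | 10.2% / 10.2% |
| 2.5%, 2.5% | 95.1% / 95.2% | 14.7% / 28.1% | 85.3% / 71.9% |

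The planned upper limit misses in 0%, 1.6% and 0% of zero-event samples. Mean width there is 2.42 points planned vs 3.97 Newcombe (1.0% in both) and 3.83 vs 4.86 (2.5% vs 1.0%).

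**A higher imiquimod rate.** Protocol 8.2.2 says: "The rate of progression to SCC was reported to be 1.6% (2/128 patients) within one year". With an assumed constant hazard, 1 − (1 − 2/128)³ = 4.6% over 3 years. At 4.6% vs 1.0% the chance of an arm without events is 9.0%. Overall coverage is 94.7% planned and 94.4% with the fallback; within zero-event samples it is about 93% and 90% to 91%.

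**The case against.** The strongest reply is that a 95% interval promises coverage over repeated trials, and over repeated trials this one keeps it: 94.2% to 95.5% at the planning rates. Judging it only in samples picked for an extreme result is severe, and Newcombe also falls short of 95% there. This stands. A reader might infer that the planned interval is invalid in general; the enumeration does not support that.

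A reader might also infer that the upper limit fails, so that the plan understates the largest plausible excess risk. The planned upper limit is shorter than Newcombe's, but it misses in at most 1.6% of zero-event samples, below the nominal 2.5%. The misses fall on the limit nearer zero. The demonstrable error is therefore an interval that can suggest a difference too readily, as at 4 vs 0.

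The stakes are also limited. The analysis is descriptive, with no margin or stopping rule attached. Shells 5 to 8 show counts and subject-years, and "numbers at risk and censoring information will be presented by treatment group", so a reader can see that an arm had no events. An interval of 0 to 0 would be recognised at once, and its chance is at most 0.8%. The 17% figure needs a rate of 1.0% in both arms; at 2.5% in both it is 0.5%. All this lowers the severity. It does not make the printed interval right, because a standard error of 0 is not a valid statement of uncertainty about a cancer risk estimated from 240 people.

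Finally, the remedy is not better on every measure. It leaves the lower-limit miss at 2.5% vs 1.0% unchanged at 10.2% and slightly lowers coverage at 4.6% vs 1.0%.

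**Conclusion.** The point holds as a low-severity correction. The SAP states a formula that gives a wrong output in a foreseeable case, and no other section repairs it. At the planning rates the case arises with probability 0.5% to 17.1%. The interval is then too narrow: at 1.0% in both arms its mean width is 2.42 points against 3.97, and its coverage 76.9% against 90.1%.

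These figures assume 240 per arm and complete follow-up; losses would make an arm without events more likely. The 4.6% scenario also assumes a constant hazard. No zero-event probability was computed for SCC plus other neoplasia. That endpoint includes every SCC, so an arm without events can only be less likely for it.

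The finding concerns the interval printed when an arm has no event. It is not evidence of poor coverage overall or of an upper limit that misses too often.

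**What to change.** Add to SAP 7.3.2: when either arm has no event by Month 36, the interval for the difference and that arm's own limits use a score-based method that is defined at zero events. One concrete choice is Newcombe's interval with Wilson limits:

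- For an arm with events, use the Kaplan-Meier estimate F with effective n = F(1−F)/SE².
- For the arm without events, use as n the number at risk when the Visit 16 window opens (Month 36 minus 28 days, Protocol 10.1.3). The number at exactly Month 36 would be a poor choice. If last visits spread evenly over the window it is about half the arm, and n = 119 instead of 240 moves the Wilson upper limit from 1.58% to 3.13%.

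Apply the rule wherever the formula is used (Tables 2-19 to 2-22).

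The cost is one or two sentences and a few lines of code. Numbers at risk are already planned output, and nothing changes unless an arm has no event. The price is conservatism at 1.0% in both arms (97.8% overall) and the small loss of coverage at 4.6% vs 1.0%.
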